### **Statistics**

Descriptive statistics will be applied to demographics, intraoperative, and postoperative data. Comparisons between groups will be performed using a 2-tailed *t*-test or Mann-Whitney U for parametric and non-parametric data as appropriate. A *p*-value of 0.05 will be used to determine statistical significance.

Primary analysis will be an intention-to-treat analysis of total MME use after surgery. Secondary analyses will evaluate effect on pain scores, patient satisfaction with pain control,

No previously published data on narcotic consumption after discharge for any minimally invasive hysterectomy (vaginal, laparoscopic, robotic) could be identified in a literature search. Chart review averaging 3 patients' data demonstrated average use of 150 MMEs after laparoscopic hysterectomy from PACU admission to hospital discharge. Assuming use of 20 oxycodone 5 mg tablets following discharge yields an additional 150 MMEs; total estimated use after laparoscopic hysterectomy is 300 MMEs. Considering a 20% MME reduction as clinically significant (8 x 5mg oxycodone pills), an alpha of 0.05, power of 90%, and SD of 100 MMEs with a 1:1 sampling ratio, 59 subjects per arm (total 118) would be required to demonstrate a statistically significant difference. Addition of a 20% margin for losses to follow up, pre- and post-randomization exclusions, 142 patients would be targeted for recruitment.

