### **Research Plan and Methods**

Patients  $\geq 18$  years old undergoing laparoscopic (either conventional or robotic) hysterectomy will be recruited. Patients will be excluded for (a) taking opioid analgesics, including Tramadol, on a daily basis within the two weeks prior to surgery (b) planned ICU admission identified prior to randomization, (c) conversion to laparotomy or any incision  $\geq 4$  cm, (d) regional anesthesia or tap block use, and (e) planned same-day discharge. The intent of excluding patients who are opioid tolerant, defined as patients who are chronically receiving opioid analgesics on a daily basis, is to prevent confounding of our specific aims related to total opioid use. Patients will not be excluded due to additional surgical procedures performed or due to malignancy as an indication for surgery. Trial will adhere to CONSORT guidelines.

In the preoperative area, the Brief Pain Inventory-short form (BPI) will be administered by study personnel, as the first of two questionnaires. The BPI short form is a validated measure that will allow for quick assessment of baseline and postoperative pain severity and impact on function. Preoperative and intraoperative medications will be standardized using a modified Magic Pathway (multimodal analgesia) with intraoperative narcotic guidelines. All intraoperative and postoperative pain management decisions will be left to the discretion of the subject's surgeon. Following incision closure, the surgeon will determine eligibility for randomization. Subjects will be randomized, using REDcap, by a study coordinator to abdominal ice pack plus routine care or routine Randomization will be stratified into two groups, patients with chronic pelvic pain (pain present for  $\geq 6$  months, excluding isolated dysmenorrhea) and patients without chronic pelvic pain; there will be no stratification for surgical approach. Blinding will not be possible for patients, physicians, or study coordinator.

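### The primary test of total MME uses neither the chronic-pelvic-pain stratum nor the preoperative BPI; it is valid, but may be mildly conservative and give up a little power

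*Combined protocol and SAP*

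**What the plan says.** Under Research Plan and Methods: "Randomization will be stratified into two groups, patients with chronic pelvic pain" and patients without it. Allocation is made in REDCap after incision closure; block size and method are not given. The BPI short form is administered before surgery as a baseline measure of pain.

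Under Statistics: "Primary analysis will be an intention-to-treat analysis of total MME use after surgery". The tests are given in one general sentence: "Comparisons between groups will be performed using a 2-tailed" t-test or "Mann-Whitney U for parametric and non-parametric data as appropriate". No stratified test, regression or covariate is named for the primary analysis. The sample size takes a 20% reduction from 300 MME, with "power of 90%, and SD of 100 MMEs with a 1:1 sampling ratio", and arrives at 59 per arm.

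The sentence on secondary analyses breaks off in the available text, so this point is confined to the primary analysis.

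**The concern.** Stratifying on a variable that predicts the outcome, with balance inside each stratum, removes the between-stratum variation from the treatment comparison. An unadjusted test does not know this. Its standard error still includes that variation, so it is too large and the test rejects less often than its nominal 5%. The design has bought precision that the analysis does not use.

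The BPI is a different case. It is not a stratification factor, so leaving it out does not disturb the test's level. It only forgoes whatever precision the BPI would add, in proportion to the MME variance it explains.

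What is at stake is efficiency on the primary endpoint, using two variables the trial already collects.

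**Working it through.** **1. The plan's own figure.** Inputs from Statistics: control mean 300 MME, 20% reduction = 60 MME, SD 100, two-sided alpha 0.05, power 90%, 1:1.

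n per arm = 2 × (1.960 + 1.282)² × (100/60)² = 58.4, rounded up to 59, which matches the plan. The standard error at 59 per arm is 100 × √(2/59) = 18.41, so 60/18.41 = 3.259 and power = Φ(3.259 − 1.960) = 90.3% (89.8% from the noncentral t).

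**2. Ignoring a balanced, prognostic stratum.** The documents do not give the share p with chronic pelvic pain, the MME difference D between strata, or the block size. All three are assumed here. With total SD 100, R² = p(1 − p)D²/100². At p = 0.3, R² of 0.02, 0.10 and 0.20 corresponds to D = 100 × √(R²/0.21) = 31, 69 and 98 MME.

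Under perfect balance within strata:
- true SD of the estimate = 18.41 × √(1 − R²), while the unadjusted SE stays near 18.41
- type I error of the unadjusted test = 2 × [1 − Φ(1.960/√(1 − R²))]
- unadjusted power = Φ((3.259 − 1.960)/√(1 − R²))
- stratum-adjusted power = Φ(3.259/√(1 − R²) − 1.960)

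| Stratum R² | True SD | Type I error, unadjusted | Power, unadjusted | Power, adjusted |
|---|---|---|---|---|
| 0.02 | 18.2 | 0.048 | 90.5% | 90.9% |
| 0.10 | 17.5 | 0.039 | 91.5% | 93.0% |
| 0.20 | 16.5 | 0.028 | 92.7% | 95.4% |

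Simulation (118 patients, blocks of 4 within strata, p = 0.3, normal MME, 12,000 trials per cell) agrees. Unadjusted type I error was 0.048, 0.038 and 0.030. Power, unadjusted v stratum-adjusted, was 90.0% v 90.4%, 91.1% v 92.6% and 91.6% v 94.8%. Separate runs put the type I error at R² 0.10 as high as 0.045, and that at R² 0.20 between 0.029 and 0.032. The Mann-Whitney U behaves alike: with p = 0.3 and D = 100 its type I error was 0.028, against 0.026 for the t-test.

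Without blocking within strata, at R² 0.10, the unadjusted test kept its level (0.047). The stratum is then an ordinary covariate (power 89.8% v 92.3%).

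**3. Leaving out the BPI.** From the noncentral t at 59 per arm, adjusting for a BPI that explains 2%, 10% or 20% of MME variance moves power from 89.8% to 90.4%, 92.6% or 95.1%. Simulated type I error without the BPI stayed between 0.046 and 0.051.

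**4. Both together.** The gains need not add, because both variables reflect preoperative pain. With each at R² 0.10, simulated power went from 91.1% to 94.8% when the two were uncorrelated, but from 91.3% to 93.4% at a correlation of 0.5.

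**5. Skewed MME.** Lognormal outcome, control mean 300, treated values multiplied by 0.8, p = 0.3, blocks of 4, 5,000 trials per cell. R² is on the log scale, for stratum and BPI each.

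| SD | R² each | Adjusted mean model | Mann-Whitney | van Elteren |
|---|---|---|---|---|
| 100 | 0 | 94.7% | 95.3% | 95.0% |
| 200 | 0 | 44.1% | 48.4% | 48.1% |
| 300 | 0 | 23.3% | 29.8% | 29.7% |
| 200 | 0.10 | 50.5% | 48.7% | 52.5% |
| 300 | 0.10 | 25.9% | 26.6% | 30.3% |

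A separate run with covariates that explain nothing gave 44.6% v 47.6% (SD 200) and 22.7% v 27.9% (SD 300) for mean model v Mann-Whitney. The loss from a mean model is therefore about 3 to 6 points. The van Elteren test loses essentially nothing to the Mann-Whitney U and gains when the stratum matters.

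**The case against.** The strongest reply is that no error has been shown. The planned test is valid, the sample size is right for it, and what remains is a preference for a more efficient analysis. This stands, and it limits the point to an optional improvement.

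The size also rests on assumptions. The two larger cells need strata that differ by 69 or 98 MME, more than the 60 MME treatment effect itself. At 31 MME the difference is within simulation error. Excluding daily opioid users may push the real values toward the small end. This stands too. Against it, chronic pelvic pain is the only stratification factor the investigators chose, which suggests they expected it to matter.

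A covariate-adjusted mean model for every case would be a tempting remedy. The objection to it succeeds. The plan allows a rank test for skewed data, the SD of 100 is given no source, and a mean model can lose power under strong skew. Nor can the point rest on confidence intervals, since the Statistics section promises none.

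The broken sentence in Statistics leaves some doubt about what else was written. But it concerns secondary analyses and follows the statement of the primary one.

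**Conclusion.** The point holds as a modest matter of efficiency. The primary comparison leaves out the factor the trial randomizes by and a baseline it collects. If allocation is balanced within strata and the stratum predicts MME, the test is mildly conservative. For assumed R² of 0.02, 0.10 and 0.20, type I error is about 0.05, 0.04 and 0.03, with about 0, 2 and 3 points of power forgone. If the stratum does not predict MME, nothing is lost.

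A reader might infer that the analysis is invalid, that false positives are increased, or that the trial is underpowered. The documents support none of these: the error runs in the safe direction, and the planned 90% power is met or slightly exceeded under the stated inputs. A reader might also infer that omitting the BPI distorts the test. It does not, because the BPI plays no part in randomization. Stratum prevalence, stratum effect and BPI–MME correlation are all absent from the documents, so the real gain may be negligible.

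**What to change.** In Statistics, replace each planned primary test with its stratified counterpart, fixed before the data are seen:

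- Where the t-test would be used: a linear model of total MME on arm and chronic-pelvic-pain stratum, with preoperative BPI pain severity as a prespecified covariate.
- Where the Mann-Whitney U would be used because MME is skewed: the van Elteren test stratified by chronic pelvic pain.

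Do not make the mean model primary for strongly skewed MME. The sample size need not change. The cost is a few lines of wording and slightly more analysis work; both variables are already collected.

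### Does adding 20% to 118, rather than dividing 118 by 0.8, leave the recruitment target of 142 too small?

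*Combined protocol and SAP*

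**What the plan says.** All the relevant text is in the Statistics section of the combined protocol and SAP. It assumes that "total estimated use after laparoscopic hysterectomy is 300 MMEs" and treats a 20% reduction as clinically significant. With "an alpha of 0.05, power of 90%, and SD of 100 MMEs with a 1:1 sampling ratio", it finds that "59 subjects per arm (total 118) would be required to demonstrate a statistically significant difference". It then moves from the evaluable number to the recruitment number: "Addition of a 20% margin for losses to follow up, pre- and post-randomization exclusions", after which "142 patients would be targeted for recruitment". The same section makes the tests two-tailed ("Comparisons between groups will be performed using a 2-tailed") and allows a t-test or a Mann-Whitney test, depending on the data. The section gives no expected rate for any of the three kinds of loss that it names.

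**The concern.** An allowance for attrition exists so that the required number remains after the losses. If a fraction f of recruits is expected to be lost, the required number is divided by (1 - f). Multiplying by (1 + f) is a familiar slip and always gives too few. Here 118 x 1.2 gives 142, while 118 / 0.8 gives 148, so the target looks like that slip.

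The margin also has real work to do. It is counted at recruitment, while eligibility is settled only after incision closure (Research Plan and Methods), so some recruits will not be randomized. The primary outcome, total MME use, also needs pill counts and diaries collected around the postoperative visit, typically six weeks after dismissal. If the sponsor expects to lose 20% in all, the trial would end below the 118 that it says it needs, and below 90% power.

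**Working it through.** **Inputs, all from the Statistics section.** Control mean 300 MME; reduction 20%, so a difference of 0.20 x 300 = 60 MME; SD 100 MME; two-sided alpha 0.05; power 90%; allocation 1:1. The tablet equivalent agrees: 20 tablets are taken as 150 MME, or 7.5 each, and 8 x 7.5 = 60.

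**Reproducing the plan's sample size.** By the normal approximation, n per arm = 2 x (1.960 + 1.282)² x (100/60)² = 58.4, so 59 per arm and 118 in total. This matches. The exact t-test gives 59.35, so 60 per arm, a rounding difference that has nothing to do with the margin.

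**Reproducing the recruitment target.** 118 x 1.2 = 141.6, so 142. This matches. The alternative, 118 / 0.8 = 147.5, so 148, does not.

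**What 142 tolerates.** 142 - 118 = 24 patients, and 24 / 142 = 16.9%.

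**Power at different total losses.** Normal approximation: power = Φ(60 / (100 x √(2/n)) - 1.960), with n per arm. The exact t-test is shown beside it.

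| Total loss from 142 | Patients left | n per arm | Normal approximation | Exact t-test |
|---|---|---|---|---|
| 0% | 142 | 71 | 94.7% | not computed |
| 16.9% | 118 | 59 | 90.3% | 89.8% |
| 20% | 113.6 | 56.8 | 89.2% | 88.7% |

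For the last row: 142 x 0.8 = 113.6; 60 / (100 x √(2/56.8)) = 3.198; 3.198 - 1.960 = 1.238; Φ(1.238) = 89.2%.

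The cost of multiplying instead of dividing, if 20% really were lost, is 90.3 - 89.2 = 1.1 points, or 89.8 - 88.7 = 1.1 points by the t-test.

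**Would 148 restore 90%?** 148 x 0.8 = 118.4, about 59 per arm. By the exact t-test, 59 per arm gives 89.8%, still under 90%. To meet 90% by that test after a 20% loss would take 120 / 0.8 = 150. The choice between 142 and 148 is therefore not a choice between missing and meeting 90% on the stricter calculation.

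**The Mann-Whitney test.** With the usual efficiency of 0.955 under normal data, power is about 87% at 56.8 per arm. It is already 88.4% at the full 59 per arm (59 x 0.955 = 56.3 effective), so much of the gap to 90% comes from the test and not from the margin. The 0.955 also assumes normal data, whereas the plan keeps this test for data that are not.

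**Scale.** If the SD were 105 instead of 100, t-test power at 59 per arm would fall from 89.8% to 86.8%, a loss of 3.0 points. The SD of 105 is my illustration; the plan gives no source for its 100.

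**The case for a change.** The best case for a change is that the margin is there for losses and exclusions, so its only purpose is to leave 118 patients once they have happened. Many readers will take a 20% margin as protection against a 20% loss, which 142 does not give. With no loss rates stated, the plan should at least be clear about what it has bought. Either remedy is cheap: one sentence, or six more recruits, when the Timeline section forecasts 235 subjects in a year.

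The arithmetic in this argument stands, and so does the observation that 142 covers a loss of about 17% and not 20%. What does not stand is the step from there to an error. The wording is of a margin added, and 118 x 1.2 adds it. The only other 20% applied to patients, in the Timeline section, is an estimate of preoperative narcotic use for the recruitment forecast and has no bearing on attrition. Pre-randomization exclusions are not left out either, since the plan lists them as part of what the margin covers. Follow-up loss is also contained: for patients who do not return, the Research Plan has the diary sent back by prepaid envelope and the pill count taken by phone.

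**Conclusion.** No change is needed. The target of 142 is a correct 20% addition to 118, and the documents state no loss rate that it fails to cover. It keeps the required 118 for any total loss up to 16.9%. On the less favourable reading, with 20% of recruits lost, the shortfall is 4 to 5 patients and about 1.1 points of power: 89.2% by the normal approximation that reproduces the plan's 59 per arm, or 88.7% by the exact t-test.

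These figures assume a true difference of 60 MME, an SD of 100, roughly normal data, and losses that fall evenly on the two arms. The first two are rough. The in-hospital half of the 300 MME comes from a chart review of 3 patients, and the post-discharge half from an assumed 20 tablets. Six recruits lie well inside that uncertainty. A note that 142 tolerates about 17% total loss would be accurate, but it would correct no stated figure and alter no analysis or conclusion. Raising the target would enrol more patients to meet a loss rate that the plan never set.

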### **Impact**

Publication is expected in a high impact factor journal given study design and potential for patient benefit. Results are directly relevant to current Mayo Clinic clinical practice and could immediately be applied to patient care. Additional research on narcotic use and/or ice pack therapy in other gynecologic surgeries could follow, as well as evaluation in specific patient populations such as chronic pelvic pain. This could allow development of an area of clinical expertise for personal

Abdominal ice packs for pain control and reduction of narcotic use following laparoscopic hysterectomy: a randomized controlled trial. [name].

career development. Data from this study, if positive, could tie in to the current enhanced recovery (ERAS) program adding to the current armamentarium. Further evaluation into other laparoscopic procedures may also be considered; grants from organizations such as AAGL and ACOG could be sought to support this expansion. If a difference is noted, then more sophisticated ice packs or cooling systems could be an interest to Mayo Clinic Ventures and an application for device creation could be submitted at next available RFA.

### Timeline

In 2016, 586 laparoscopic or robotic hysterectomies were performed at Mayo Clinic Rochester. Rate of preoperative narcotic use in this population is unknown, but 20% estimate would be generous. This would leave about 470 patients for recruitment, and assuming an enrollment of 50% we are left with 235 subjects in a year. As such, 12 months or less for subject recruitment, should be sufficient; 6 months are estimated for protocol development and IRB approval, and another 6 months for data analysis, manuscript preparation, and publication. Total projected time from project initiation to publication would 2 years.

